EQ5D — the EuroQol-5D, an instrument developed in Europe and widely used, which evaluates the generic quality of life.

F, FR — French (size)

FIH — first-in-human

GI — Gastrointestinal

Hb — hemoglobin

HCPCS — The Healthcare Common Procedure Coding System

Hct — hematocrit

HFpEF — heart failure with preserved ejection fraction

HFREF — heart failure with reduced ejection fraction

HFmEF— heart failure with mid-range ejection fraction

Hgb — hemoglobin

HIPAA — Health Insurance Portability and Accountability Act

HIT — Heparin Induced Thrombocytopenia

HITRUST — a privately held company located in Frisco, Texas, that, in collaboration with The HITRUST CSF is a prescriptive set of controls that was designed to meet the requirements of multiple regulations and standards provides a way to comply with standards such as ISO/IEC 27000-series and HIPAA.

HR — heart rate

HR-PCI — high risk percutaneous coronary intervention

IABP — intra-aortic balloon pump

ICD-10 — 10th revision of the International Statistical Classification of Diseases and Related Health Problems, a medical classification list by the World Health Organization

ICH — International Council on Harmonisation of Technical Requirements for Registration of Pharmaceuticals for Human Use

ICMJE — International Committee of Medical Journal Editors

ID — inner diameter

IEC — independent ethics committee

INR — International Normalized Ratio

INTERMACS — Interagency Registry for Mechanically Assisted Circulatory Support

IRB — Institutional Review Board

IS — Introducer Set

ISO 14155 — Clinical investigation of medical devices for human subjects – Good clinical practice

IT — Information Technology

IU/L — International Units Per Litre

IV — intravenous

KCCQ — Kansas City Cardiomyopathy Questionnaire

LA — left atrial

LDH — lactate dehydrogenase

LFTs — liver function test

LVAD — left ventricular assist device

LVEDV — left ventricular end-diastolic volume

LVESD — left ventricular end-systolic dimension

LVESV — left ventricular end-systolic volume

MAP — mean arterial pressure

MCS — mechanical circulatory support

MR — mitral regurgitation

NSAIDS — nonsteroidal anti-inflammatory drugs

NT-pro-BNP — N-terminal pro b-type Natriuretic Peptide

NYHA — New York Heart Association

OD — outer diameter

PA — pulmonary artery

PAC — pulmonary artery catheter

PAP — pulmonary artery pressure

PCWP — pulmonary capillary wedge pressure

pfH — Plasma free hemoglobin

PICF — patient information and consent form

QoL — quality of life

RBCs — red blood cells

RPM — revolutions per minute (1,000 RPM = 1KRPM)

RR — respiratory rate

RVIDD — right ventricular internal diameter in diastole

SADE — serious adverse device effect

SAE — serious adverse event

SSAE 16 — Statement on Standards for Attestation Engagements no. 16

SV — stroke volume

TAPSE — tricuspid annular plane systolic excursion

TAVR — transcatheter aortic valve replacement

TLS — transport layer security

TR — tricuspid regurgitation

UADE — unanticipated adverse device effect

UFH — unfractionated heparin

UOP — urine output

USADE — unanticipated serious adverse device effect

VAD — ventricular assist device

VARC — The Valve Academic Research Consortium

WRF — worsening renal function

Summary and General Information

Title:	The Aortix CRS Pilot Study: An Evaluation of the Safety and Performance of the Aortix System for Intra-Aortic Mechanical Circulatory Support in Patients with Cardiorenal Syndrome
Investigational Plan:	PVP017
Investigational Device:	The Aortix System
Study Design & Purpose:	The study is a prospective, multi-center, non-randomized feasibility study to evaluate the safety and performance of the Aortix System in patients hospitalized with acute decompensated heart failure (ADHF) irrespective of ejection fraction and worsening renal function refractory to medical management with persistent congestion.
Objectives:	
To evaluate the Aortix System, specifically to assess:
 
▪ Safety:
○ Observe the nature, severity, and frequency of adverse events associated with the delivery, use, and retrieval of the Aortix Pump.▪ Performance:
○ Successfully deliver the Aortix Pump to the descending thoracic aorta using the Aortix Delivery System;○ Aortix Pump shall function as programmed for the duration of therapy;○ Manage the Aortix Pump Power Lead and access site over the course of therapy without significant complications;○ Successfully retrieve and remove the Aortix Pump using the Aortix Retrieval System.▪ Effectiveness:
○ Evaluate hemodynamic decongestion (CVP, PCWP) during Aortix therapy;○ Evaluate the effect of the Aortix therapy on kidney function;○ Evaluate the impact of the Aortix Pump on clinical biomarkers of congestion.
Patient Population:	This study will enroll up to 60 patients in order to treat 30 patients using Aortix with ADHF (irrespective of ejection fraction) refractory to medical management with persistent clinical signs of congestion and worsening renal function.

- Inclusion Criteria:
- 1) Admitted to the hospital with a primary diagnosis of acute decompensated heart failure, either heart failure with reduced or preserved ejection fraction (HFrEF, HFpEF or HFmEF);
 - 2) Worsening renal function (serum creatinine increase by ≥ 0.3 mg/dl [≥ 27 $\mu\text{mol/L}$]) despite 48 hours of intravenous diuretic therapy. Increase can be compared to a baseline value taken within 90 days of hospitalization or during hospitalization;
 - 3) Objective measure of congestion (Elevated PCWP [≥ 20 mmHg] OR Elevated CVP [≥ 12 mmHg]) obtained via catheter measurement;ⁱ
 - 4) Persistent clinical signs and/or symptoms of congestion despite diuretic therapy (one or more of the following):
 - a) dyspnea at rest or with minimal exertion,
 - b) paroxysmal nocturnal dyspnea,
 - c) orthopnea,
 - d) lower extremity edema ($\geq 2+$),
 - e) elevated jugular venous pressure,
 - f) pulmonary rales,
 - g) enlarged liver or ascites,
 - h) pulmonary vascular congestion on chest x-ray;
 - 5) Age > 21 years and able to provide written informed consent.

- Exclusion Criteria:
- 1) Treatment with high dose IV inotropes within the last 48 hours. High dose is defined as > 1 unit of inotrope (excluding digoxin) as follows:
5 $\mu\text{g/kg/min}$ dopamine = 1 unit,
5 $\mu\text{g/kg/min}$ dobutamine = 1 unit,
0.375 $\mu\text{g/kg/min}$ milrinone = 1 unit,
(for example, dopamine 2.5 $\mu\text{g/kg/min}$ + dobutamine 2.5 $\mu\text{g/kg/min}$ = 1 unit; dobutamine 2.5 $\mu\text{g/kg/min}$ + milrinone 0.1875 $\mu\text{g/kg/min}$ = 1 unit);
 - 2) Treatment with vasopressors to maintain blood pressure as per exclusion #3;
 - 3) Active and ongoing hypotension defined as a systolic blood pressure < 90 mmHg lasting more than 30 minutes or a mean arterial pressure (MAP) < 60 mmHg lasting more than 30 minutes;
 - 4) Acute Kidney Failure defined as increase in serum creatinine to ≥ 4.0 mg/dL (≥ 353.6 $\mu\text{mol/L}$) within the last 48 hours before enrollment;
 - 5) Exposure to intravenous contrast, aminoglycosides or high dose NSAIDS in the 48 hours before enrollment;
 - 6) Known or suspected contrast induced nephropathy;

ⁱ This assessment requires patient to sign informed consent.

- 7) Prior kidney transplant, isolated single kidney, stage V Chronic Kidney Disease (eGFR \leq 15) at admission OR use of dialysis, continuous renal replacement therapy (CRRT) or aquapheresis (ultrafiltration) in last 90 days;
- 8) Urologic intervention (except indwelling urinary (Foley) catheter)) within the last 7 days;
- 9) Known cirrhosis or shock liver;
- 10) Presence of an active infection;
- 11) Prior heart transplant in the last 2 years, heart failure due to rejection of a previous heart transplant, planned heart transplantation before the 30-day follow-up visit;
- 12) Current or previous support with a durable LVAD at any time or use of an intra-aortic balloon pump, extracorporeal membrane oxygenation (ECMO), or percutaneous ventricular assist devices (e.g. Impella or TandemHeart) currently or within the last 30 days;
- 13) Patient has known hypo- or hyper coaguable state such as disseminated intravascular coagulation or heparin induced thrombocytopenia (HIT);
- 14) Known cardiac amyloidosis;
- 15) Acute myocardial infarction Type 1 within 30 days of enrollment, or planned coronary revascularization;
- 16) Stroke within 30 days of enrollment;
- 17) Severe Bleeding Risk (any of the following):
 - a) Previous intracranial bleed unless there is documentation in the medical record (from a physician that is not part of the study) that the patient can safely use anticoagulation for 7 days,
 - b) GI bleeding within 6 months requiring hospitalization and/or transfusion,
 - c) Recent major surgery within 6 months if the surgical wound is judged to be associated with an increased risk of bleeding,
 - d) Endovascular procedure with ilio-femoral access > 6 FR within 30 days,
 - e) Platelet count <75,000 cells/mm³,ⁱⁱ
 - f) Uncorrectable bleeding diathesis or coagulopathy (e.g. INR \geq 2 not due to anticoagulation therapy);
- 18) Current endovascular stent graft in the descending aorta or any femoro-iliac vessels;
- 19) Contraindicated Anatomy:ⁱⁱⁱ
 - a) Descending aortic anatomy that would prevent safe placement of the device [$<$ 18mm or $>$ 31mm aorta diameter at deployment location

ⁱⁱ If patient doesn't have a, b, c, d or f, but the platelet count at time of enrollment is <75,000 cells/mm³, patient can be enrolled and the platelet count re-assessed at the time of the procedure. The platelet count at time of procedure should be \geq 75,000 cells/mm³. If platelet count at time of procedure is <75,000 cells/mm³, patient would be a screen failure.

ⁱⁱⁱ Anatomy assessment requires patient to sign informed consent.

(measured between the superior aspect of the T10 vertebra and superior aspect of the L1 vertebra)],

- b) Ilio-femoral diameter or peripheral vascular anatomy that would preclude safe placement of a 21F (outer diameter) introducer sheath,
 - c) Abnormalities or severe vascular disease that would preclude safe access and device delivery (e.g. aneurysm with thrombus, marked tortuosity, significant narrowing or inadequate size of the abdominal aorta, iliac or femoral arteries, or severe calcification),
 - d) Known connective tissue disorder (e.g. Marfan Syndrome) or other aortopathy at risk of vascular injury;
- 20) Known hypersensitivity or contraindication to study or procedure medications (e.g. anticoagulation therapy) or device materials (e.g. history of severe reaction to nickel or nitinol);
- 21) Positive pregnancy test if of childbearing potential;
- 22) Participation in any other clinical investigation that is likely to confound study results or affect the study;
- 23) Unable or unwilling to undergo screening (imaging, PA Catheter placement), device implant and retrieval procedures.

Follow-up
schedule:

Patients with the pump successfully implanted will be followed for 30 days (± 7 days) post device retrieval for protocol required data collection. Patients with the pump implanted will be followed for adverse events for 30 days (± 7 days) post device retrieval. Patients that have an attempted implant but do not have the pump implanted will be followed for adverse events for 30 days (± 7 days) post attempted implant. If implanted or attempted implant patients are still hospitalized at 30 days due to an adverse event relating to the device or any study related procedures, they must be followed until resolution of the adverse event, resolution with sequelae, or until a terminal event.^{iv} Patients who are enrolled and undergo anatomy screening and/or invasive hemodynamic measurements who do not have an attempted implant will be followed for adverse events for 7 days (± 2 days) post anatomic screening or invasive hemodynamics (whichever is later) or until hospital discharge, whichever is first.

Study Duration:

It is expected that study patients will be enrolled over a period of approximately 12-24 months within Australia and the USA. The total duration of a patient's participation in the study is approximately 1.5 months including screening, enrollment, therapy and follow-up.

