4.8 Follow-Up

Patients with the pump implanted will be followed for adverse events for 30 days (± 7 days) post device retrieval. If implanted patients are still hospitalized at 30 days due to an adverse event relating to the device or any study related procedures, they must be followed until resolution of the adverse event, resolution with sequelae, or until a terminal event. Protocol required data collection for patients with the pump implanted will be for 30 days post device retrieval (± 7 days) per **Appendix A**.

The following data will be collected:

- NYHA classification
- Cardiovascular exam (edema, pulmonary auscultation, weight),
- Vital signs (HR, BP, RR)
- Dyspnea evaluation
- KCCQ, EQ5D
- Document current cardiovascular/renal medications and adverse events
- Blood and urine labs per **Appendix A**

Patients that have an attempted implant but do not have the pump implanted will be followed for adverse events for 30 days (± 7 days) post attempted implant. If attempted implant patients are still hospitalized at 30 days due to an adverse event relating to the device or any study related procedures, they must be followed until resolution of the adverse event, resolution with sequelae, or until a terminal event.

Terminal events are death, LVAD implantation, heart and/or kidney transplantation, dialysis, ultrafiltration or CRRT.

Patients who are enrolled and undergo anatomy screening and/or invasive hemodynamic measurements who do not have an attempted implant will be followed for adverse events for 7 days (\pm 2 days) post anatomic screening or invasive hemodynamics (whichever is later) or until hospital discharge, whichever is first.

Every attempt should be made to perform follow-up visits in person. Should extenuating circumstances (e.g., COVID-19 global pandemic travel restrictions) impact a site's ability to perform follow-up visits in person, notify the sponsor and make every attempt to collect the protocol required data via other means (e.g., telephone, video conference, blood and urine labs at a non-hospital lab).

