For this clinical study, adverse events will be collected post informed consent when invasive or non-standard-of-care screening begins (i.e. imaging or invasive hemodynamics). For safety reporting, all adverse events will be reported until the patient exits the study. Any unresolved procedural or device related adverse events that are still ongoing past study exit will be reported as being unresolved or unresolvable.

Enrollment will pause if any of the following serious, procedure related adverse events occur:

- Death (Aortix procedure related only)
- Aortic Injury Requiring Surgical Intervention to Repair (Aortix procedure related only)

Enrollment will be paused until the event can be evaluated and discussed with regulatory agencies if appropriate and approval is granted to continue enrollment.

For purposes of this study, minor clinical changes which would normally occur for this patient during the course of having heart failure which are not related to the device, the procedure or the therapy, need not be reported. Examples include but are not limited to ongoing poor appetite, weakness or fatigue. Investigator discretion is expected. If unsure, report as an adverse event.

It is anticipated that due to underlying baseline conditions, all laboratory values may not remain in the range of normal for a given participant. Investigator discretion is required to determine if a laboratory value that remains out of range is associated with an untoward clinical finding that should be reported as an adverse event.

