6.2 Adverse Event Definitions

Adverse Event (AE): Any untoward medical occurrence, unintended disease or injury, or untoward clinical signs (including abnormal laboratory findings) in participants, users, or other persons, whether or not related to the investigational medical device.

Note: This definition includes events related to the investigational medical device or the comparator. This definition includes events related to the procedures involved. For users or other persons, this definition is restricted to events related to investigational medical devices.

Adverse Device Effect (ADE): Adverse event related to the use of an investigational medical device.

Note: This definition includes adverse events resulting from insufficient or inadequate instructions for use, deployment, implantation, installation, or operation, or any malfunction of the investigational medical device. This definition includes any event resulting from use error or from intentional misuse of the investigational medical device.

Serious Adverse Event (SAE):

A Serious Adverse Event is an adverse event that:

- a. led to death
- b. led to serious deterioration in the health of the participant, that either resulted in:
 - a life-threatening illness or injury, or
 - a permanent impairment of a body structure or a body function, or
 - prolonged hospitalization, or
 - medical or surgical intervention to prevent life-threatening illness or injury or permanent impairment to a body structure of a body function

Note: Planned hospitalization for a pre-existing condition, or a procedure required by the Clinical Investigation Plan, without serious deterioration in health, is not considered a serious adverse event.

Serious Adverse Device Effect (SADE): An adverse device effect that has resulted in any of the consequences characteristic of a serious adverse event.

Device Deficiency: Inadequacy of a medical device with respect to its identity, quality, durability, reliability, safety, or performance.

Note: Device deficiencies include malfunctions, user errors, and inadequate labeling. They can be, but do not have to be, associated with an ADE or AE. Device deficiencies also include effects of electromagnetic interference (EMI). EMI effects can be intermittent; EMI related device effects, degradations, or malfunctions should be reported.

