Acute kidney injury (AKIN classification) Stage 2	
 Increase in serum creatinine** to 200%-300% (2.0-3.0 fold increase compared with baseline) OR Urine output <0.5 mL/kg/h for >12 h
Acute kidney injury (AKIN classification) Stage 3†	
 Increase in serum creatinine** to >300% (>3 × increase compared with baseline) OR serum creatinine of ≥4.0 mg/dL (≥354 mmol/L) with an acute increase of at least 0.5 mg/dL (44 mmol/L) OR Urine output <0.3 ml/kg/h for ≥24 h OR Anuria for ≥12 h
Major vascular complication	
 Any aortic dissection, aortic rupture, annulus rupture, left ventricle perforation, or new apical aneurysm/pseudoaneurysm OR Access site or access-related vascular injury (dissection, stenosis, perforation, rupture, arterio-venous fistula, pseudoaneurysm, hematoma, irreversible nerve injury, compartment syndrome, percutaneous closure device failure) leading to death, life-threatening or major bleeding,‡ visceral ischemia, or neurological impairment OR Distal embolization (noncerebral) from a vascular source requiring surgery or resulting in amputation or irreversible end-organ damage OR The use of unplanned endovascular or surgical intervention associated with death, major bleeding, visceral ischemia or neurological impairment OR Any new ipsilateral lower extremity ischemia documented by subject symptoms, physical exam, and/or decreased or absent blood flow on lower extremity angiogram OR Surgery for access site-related nerve injury OR Permanent access site-related nerve injury

Minor vascular complication	
 • Access site or access-related vascular injury (dissection, stenosis, perforation, rupture, arterio-venous fistula, pseudoaneurysms, hematomas, percutaneous closure device failure) not leading to death, life-threatening or major bleeding,[‡] visceral ischemia, or neurological impairment OR • Distal embolization treated with embolectomy and/or thrombectomy and not resulting in amputation or irreversible end-organ damage OR • Any unplanned endovascular stenting or unplanned surgical intervention not meeting the criteria for a major vascular complication OR • Vascular repair or the need for vascular repair (via surgery, ultrasound-guided compression, transcatheter embolization, or stent-graft)

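### A device- or procedure-related event open at the 30-day visit is followed to its outcome only if it is keeping the patient in hospital, so outcomes in discharged patients are lost and a few events that turn on permanence may stay ungraded

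*Protocol*

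**What the plan says.** For implanted patients, Section 4.8 sets the ordinary end of observation: "Patients with the pump implanted will be followed for adverse events for 30 days" (±7) after retrieval. Patients with an attempted but failed implant have the same length of follow-up, counted from the attempt.

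The extension beyond that visit is conditional. Section 4.8 opens it with "If implanted patients are still hospitalized at 30 days due to an adverse event relating to the device or any study related procedures", and a parallel sentence covers attempted implants. Those patients are followed until the event resolves, resolves with sequelae, or a terminal event occurs. The synopsis has the same rule: if implanted or attempted-implant patients are "still hospitalized at 30 days due to an adverse event relating to the device or any study related procedures, they must be followed" to one of those end points.

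Section 6 deals with everyone else. It states that "all adverse events will be reported until the patient exits the study", and then: "Any unresolved procedural or device related adverse events that are still ongoing past study exit will be reported as being unresolved or unresolvable".

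Two sets of definitions use the eventual outcome. In Section 6.2, one of the alternative criteria for a serious adverse event (SAE) is "a permanent impairment of a body structure or a body function". In Appendix C, a major vascular complication includes "Permanent access site-related nerve injury", and it includes non-cerebral distal embolization "requiring surgery or resulting in amputation or irreversible end-organ damage".

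SAP 7.8.1 computes both primary safety percentages, for SAEs and for serious procedure-related adverse events (SPRAEs), in the As-Treated population from the clinical events committee (CEC) classification. Each patient is counted once per endpoint. Neither SAP 7.8.1 nor 7.9.1 says how an event of unknown outcome is to be classified.

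**The concern.** The extension rule accepts that day 30 can be too early to know how a related injury ends. It then applies that only where the injury is the reason for a continuing hospital stay. A patient at home or in rehabilitation with an open related injury is outside the rule. As worded, so is an inpatient kept in for heart failure whose open device injury is not the reason for the stay.

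What is at stake is mainly safety information. The safety objective is the nature, severity and frequency of events, and Section 5.2 describes this as the first human use of the pump for more than 90 minutes, with the likelihood of the risks unknown. How a lasting injury ends is part of its severity. A second, smaller stake is classification: where permanence is the deciding criterion, the CEC may have to judge it on data that stop between day 23 and day 37.

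**Working it through.** The rule rests on no event rate, power or margin, and the sample size is declared not to be statistically derived, so there is no planned figure to reproduce. The check is textual, followed by one piece of arithmetic.

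**Step 1. Is a discharged patient covered elsewhere?**
- Section 3.6 offers telephone or record contact, but to patients considering withdrawal.
- Section 4.8 allows remote collection, but for follow-up visits under extenuating circumstances.
- Section 6.3 lets the CEC ask for more source documents and hold an event as pending. It does not require new outcome data to be generated after exit.

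No provision extends follow-up for a discharged patient with an open related event.

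**Step 2. Which classifications depend on the later outcome?**

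| Event | Routes that do not need permanence | What is left to permanence |
|---|---|---|
| Any event, SAE status (6.2) | Death, life-threatening illness or injury, prolonged hospitalization, intervention to prevent such harm | An event meeting none of these |
| Access-site nerve injury (App. C) | Surgery for it is major. Neurological impairment resulting from a listed access-related vascular injury is also major | An unoperated injury with no other major feature: major if permanent, and nerve injury is not named in the minor list |
| Distal embolization (App. C) | Surgery or amputation is major | A case with neither: major only if end-organ damage is irreversible. The minor category requires that it is not |
| New ipsilateral leg ischemia (App. C) | Major on symptoms, examination or angiogram | Nothing |

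The dependence is real but narrow. Limb ischemia is not an example of it.

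**Step 3. Which of these can move a primary rate?** The event must be in an implanted patient, because SAP 7.8.1 uses the As-Treated population. The patient must also have no other qualifying SAE (or SPRAE), because each patient counts once.

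**Step 4. Effect of one patient.** With n = 30 implanted, 1/30 = 3.3 percentage points. Exact (Clopper-Pearson) 95% intervals, for illustration:

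| Patients with event | Percentage | 95% interval |
|---|---|---|
| 0/30 | 0% | 0 to 11.6 |
| 1/30 | 3.3% | 0.1 to 17.2 |
| 2/30 | 6.7% | 0.8 to 22.1 |
| 3/30 | 10.0% | 2.1 to 26.5 |

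One reclassified patient is small against this imprecision. The expected number of such patients cannot be computed, because the documents give no rate of related events open at day 30 in discharged patients.

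**The case against.** The rule is stated openly and in the same way in the synopsis, Section 4.8 and Section 6. It is a design choice in a 30-patient feasibility study, not a contradiction. An investigator or the CEC may judge permanence at the visit. The CEC may modify or add definitions (Section 6), and its charter and the case report form are not available here. The form may already separate unresolved from unresolvable events. All of this stands, and it limits the size of the point. It does not supply outcome data for a patient who has left the study.

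Three stronger readings are tempting, and the documents do not support them:
- *That the primary rates are biased because the same injury is graded by discharge status.* Patients who get the extension are in hospital because of the event, so they will ordinarily be serious through prolonged hospitalization. Longer follow-up would seldom decide their SAE status. Any uneven grading is confined to the events in the third column of the Step 2 table.
- *That the major/minor vascular split is an endpoint at risk.* It is not a named endpoint in Protocol 3.3 or SAP 5.
- *That the effect can be sized from the 5.9% to 15% in Section 5.2.* Those are all major vascular complications in valve trials, whatever made them major. They say nothing about how many cases would turn on permanence.

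A fair objection also applies to one possible remedy. Updating outcomes until the last CEC meeting would, with 12 to 24 months of enrollment, give early patients much longer than late ones to be declared permanently injured. The cut-off therefore has to be the same for all patients.

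**Conclusion.** The gap is in the text: past the 30-day visit, follow-up of a related event depends on hospitalization because of it, and other open related events are closed without an outcome. The certain consequence is loss of outcome information on injuries from a device with little human exposure. The possible further consequence is an undetermined classification for events that turn on permanence or irreversibility alone, at 3.3 points per reclassified patient in a primary safety percentage.

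This rests on 30 implanted patients and on no unseen document, such as the CEC charter, already requiring outcome updates after exit. How often it would happen is unknown, and a material distortion of the primary endpoints should not be inferred. It is a cheap improvement worth making.

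**What to change.** 1. In the synopsis Follow-up schedule and in Section 4.8, change the trigger from being in hospital because of a related event to having an unresolved device- or study-procedure-related event at the 30-day visit, in or out of hospital.
2. Follow such events by telephone or medical records until resolution, resolution with sequelae, a terminal event, or one fixed later contact. Set the timing of that contact in advance and make it the same for all patients. Align the closing rule in Section 6.
3. Keep the primary SAE and SPRAE percentages as classified at the 30-day visit. In the SAP, report the later outcome alongside, with a sensitivity count that treats still-open events as permanent.
4. Record *unresolved* and *permanent* as separate outcomes.
5. In the same revision, reconcile the SAP's window (30 days after implant, 7.8.1) with the protocol's visit (30 days after retrieval), so that the 30-day classification refers to one date.

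The cost is new protocol and consent wording, a short SAP addition, and telephone or record checks in what should be a few patients. Those patients would exit later than the stated 1.5 months.
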